4.6. STATISTICAL ANALYSIS

Descriptive statistics will be used to characterize the overall cohort and subgroups of interest. Summary statistics, including mean (standard deviation), median (interquartile range [IQR]), and frequencies will be calculated. Graphical methods will be used to examine distributions, identify potential influential points and guide in data transformations as needed. Relationships between variables will be similarly assessed for linearity, symmetry, and homoscedasticity. To compare subgroups within the larger cohort or to other cohorts, both univariate testing (e.g., using t-tests, analysis of variance [ANOVA], Kruskal-Wallis, Mann-Whitney as appropriate) and model-based adjustment for other factors will be performed. Both logistic regression and a mixed model approach with center as a random effect (to account for between-center differences) will be used as they are suited for cross-sectional and retrospective case-control analyses of multiple exposures and/or biomarkers. Comparisons between the Screening Log and enrolled patients will allow assessment of the extent of recruitment and consent bias in the sample.

Outcome measures for the many possible research aims will include, for example, measures of disease activity (e.g., complete remission defined as proteinuria <300mg/day adjusted for body surface area, change in proteinuria, or change in urine protein/creatinine ratio); measures of eGFR (e.g., time to a fixed eGFR loss, time to 40% or 50% reduction in eGFR, and eGFR slope); time to ESKD or death; time to cause-specific events (e.g., infection, thrombosis, malignancy); and PRO measures. Changes in continuous outcomes, such as urine protein and eGFR, will be graphically depicted using restricted cubic splines. Semi-parametric models will be constructed to identify distinct subgroups within the population based on clusters of trajectories. Events such as proteinuria remission, GFR slope, and 50% decline in eGFR will also be described.

To identify predictors of renal and non-renal outcomes, including therapeutic response, time-to-event analyses will be performed. Potential predictors may include clinical characteristics, genetic markers, and/or novel biomarkers. Analyses of longitudinal factors, e.g., a slope or change of a factor over time, would involve non-intersecting measurement periods for the predictor factor and follow-up periods for the outcome. Mixed longitudinal regression models will be applied for disease progression measures such as eGFR. Patient-level identifiers will be included as a random effect in these models. Time-to-

384 event Cox regression models will be used when analyzing defined outcomes and will use left truncation
385 to allow each patient's experience to contribute to the time period after biopsy that corresponds to
386 their study follow-up period. For factors likely to be influenced by treatment-by-indication bias, we will
387 evaluate whether techniques such as instrumental variables analysis are appropriate. Predictive power
388 of the model will be evaluated using log-likelihood tests and, when evaluating analyses where absolute
389 predictive accuracy is more important than relative predictive accuracy, the c-statistic. Other
390 approaches, including the net reclassification index may also be used as appropriate.

391
392 Special consideration will be applied when analyzing molecular biomarkers. For example, to screen a
393 large number of potential predictors without losing analytical power, analyses will be performed in a
394 hypothesis-generating manner. Regression analysis will be performed to obtain p-values for the
395 association of outcome with a biomarker, and a threshold value of false discovery rate would be set to
396 determine a pool of potentially important biomarkers. Selected biomarkers will be analyzed and
397 grouped according to the relevance of their biological functions. Panels will be further tested for the
398 association with outcome via ridge regression.

399
400

401 **5. HUMAN SUBJECTS**

402 **5.1. PROTECTION OF HUMAN SUBJECTS**

403 **5.1.1. Institutional Review Board**

404 This study and analysis will be performed under IRB oversight. Prior to the initiation of the study, an IRB
405 approval for study of human subjects will be obtained separately from the IRB of each of the PCCs and
406 the Data Coordinating Center (DCC). Revisions to the study protocol and changes in the study design will
407 also be submitted to the individual IRBs for approval prior to implementation.

408
409 Subjects will be enrolled in the protocol with full informed consent which will include the gathering of
410 protected health information (PHI), the collection of blood and urine specimens beyond that normally
411 performed for clinical care, sharing of archived kidney tissue specimens collected for routine clinical care,
412 and the collection of medical and PRO information at defined intervals.

413

414 **5.1.2. Patient Confidentiality**

415 Special procedures for ensuring patient confidentiality will be implemented. Data transmission and the
416 distributed data systems have multiple layers of security, as discussed below in Section 7, Study
417 Management. Each study subject will be assigned an identification number. Only this number will be
418 used to identify subjects in any individual tabulation. The PHI that is collected will represent the
419 minimum necessary to successfully execute the study.

420

421 Personally identifying information, such as name and e-mail address entered into the database at the
422 site level, will only be visible to study personnel accessed through a triple password regimen. The
423 information is encrypted at the site level. Site personnel have the decryption key, and it is not available
424 to the DCC. It is expected that only group data will be published. If individual subject data are to be
425 published, no identifying information will be included. The study files will be maintained in a secure
426 location as described below. Access to computerized data will be restricted to study personnel.
427 Password authorization will be enforced.

428

429 Authorized representatives of the Sponsor, the National Institute of Diabetes and Digestive and Kidney
430 Diseases (NIDDK), National Institutes of Health (NIH), participating clinical institutions, DCC monitoring

431 staff, as well as the IRB, have access to medical records and records from participation in this study.
432 Such access is necessary to ensure the accuracy of the findings.

433

434 5.1.2.1. Certificate of Confidentiality

435 To help protect participant privacy, a Certificate of Confidentiality will be obtained from the NIH. With
436 this Certificate, the researchers cannot be forced to disclose information that may identify a study
437 participant, even by a court subpoena, in federal, state, or local civil, criminal administrative, legislative
438 or other proceedings. The researchers will use the Certificate to resist any demands for information that
439 would identify a subject, except as explained below.

440

441 The Certificate cannot be used to resist a demand for information from personnel of the United States
442 Government that is used for auditing or evaluation of federally funded research projects or for
443 information that must be disclosed in order to meet the requirements of the federal Food and Drug
444 Administration (FDA).

445

446 Even with the Certificate of Confidentiality, the investigators continue to have ethical and legal
447 obligations to report child abuse or neglect and to prevent an individual from carrying out threats to do
448 serious harm to themselves or others. If keeping information private would immediately put the study
449 participant or someone else in danger, the investigators will release information to protect the
450 participant or another person.

451

452 5.1.3. Informed Consent

453 The consent process may differ somewhat by PCC, according to local IRB guidelines. Participants will be
454 asked to complete all study procedures. However, each study participant is able, during any study visit,
455 to decline one or more of the data collection procedures without withdrawing from the study.

456

457 Each PCC will prepare an informed consent document following the template provided by the DCC and
458 modified to meet their local IRB requirements. The initial informed consent document will be signed and
459 dated by the participant before initiation of any study-related activity.

460

461 Before obtaining a potential participant's signature on the informed consent document, the local study
462 investigator or his/her designee will review the details of the consent form orally with the potential
463 participants and answer any questions the participant has concerning involvement in the study. The
464 original signed consent form will be stored at the PCC, and a copy of the signed consent form will be
465 given to the participant.

466

467 5.1.4. Risks to the Patient

468 Patients enrolled in this study will experience more than the normal amount of testing that is customary
469 for their clinical care. Additional time will be required for the gathering of medical and PRO information.
470 Blood and urine will be collected and stored for special tests and archival storage which are not normally
471 required for clinical care. Venipuncture carries risks of pain and bruising at the puncture site. There is
472 also a risk of anxiety and a small risk of dizziness associated with blood draws.

473

474 5.1.5. Unauthorized Data Release

475 There is always the theoretical possibility of unauthorized release of Health Insurance Portability and
476 Accountability Act (HIPAA) PHI about subjects. Such disclosure would be extremely unlikely to involve a
477 threat to life, health, or safety but would be a serious invasion of the subject's privacy. It is conceivable
478 that such disclosure could have psychological, social, or legal effects on the patient. The standard

479 security procedures will effectively minimize the risk of unauthorized disclosure of data. All study
480 personnel who have access to patient data will be educated regarding the need to protect
481 confidentiality and the procedures to be followed to ensure such protection. All relevant staff will also
482 be required to sign a medical record confidentiality agreement. The computer systems on which data
483 are maintained use password protection procedures to prevent access by unauthorized users. Data to
484 be used for analysis will contain only the assigned identification numbers.

485

486 5.1.5.1 Adverse Event Monitoring

487 • **Definition of Adverse Event:** An adverse event (AE) is any untoward medical occurrence or
488 unfavorable and unintended sign in a research subject that occurs during or as a result of a
489 research procedure. For this study, the majority of the procedures are standard clinical care, and
490 adverse effects of clinical care will be tracked as complications but will not be considered
491 adverse study events. Each center will review the list of study procedures and identify the
492 specific procedures that are not standard-of-care at their institution, and these will be
493 considered research procedures. Complications that are a result of research procedures will be
494 reported and tracked as AEs.

495

496 • **Assessment of Event Severity and Relationship to Study Procedure/Treatment:** The modified
497 World Health Organization (WHO) grading system will be used for grading severity of AEs (See
498 Manual of Procedures). For AEs not covered by the modified WHO grading system, the following
499 definitions will be used:

500

Mild:	Awareness of sign, symptom, or event, but easily tolerated
Moderate:	Discomfort enough to cause interference with usual activity, and may warrant intervention
Severe:	Incapacitating with inability to do usual activities or significantly affects clinical status, and warrants intervention
Life-threatening:	Immediate risk of death

501

502 The investigator must also assess the relationship of any AE to the research procedure, based on
503 available information, using the following guidelines:

504

Unlikely related:	No temporal association, or the cause of the event has been identified; or the procedure cannot be implicated
Possibly related:	Temporal association, but other etiologies are likely to be the cause; however, involvement of the procedure cannot be excluded
Probably related:	Temporal association; other etiologies are possible, but unlikely

505 • **Definition of Serious Adverse Events:** A serious AE (SAE) is any adverse experience that results in
506 any of the following outcomes:

507

- Death;

- 508 ▪ Life-threatening AE (i.e., one that places the subject, in the view of the investigator,
509 at immediate risk of death from the AE as it occurs);
- 510 ▪ Persistent or significant disability/incapacity;
- 511 ▪ Required in-patient hospitalization, or prolonged hospitalization;
- 512 ▪ Congenital anomaly or birth defect.
- 513 ▪ Additionally, important medical events that may not result in death, be life-
514 threatening, or require hospitalization may be considered an SAE when, if based
515 upon appropriate medical judgment, they may jeopardize the subject and may
516 require medical or surgical intervention to prevent one of the outcomes listed in this
517 definition.

- 518
- 519 • **Reporting Responsibility:** Only AEs possibly or probably related to this observational study must
520 be recorded. Events related to the disease or therapy of the patient need not be reported as
521 *Observational Study-Related* AEs. The onset and end dates, severity, and relationship to study
522 procedure(s) will be recorded for each AE. Any action or outcome (e.g., hospitalization,
523 additional therapy, etc.) will also be recorded for each AE. Subjects will be questioned and/or
524 examined by the investigator or his/her designee for evidence of AEs.

525

526 All AEs and SAEs reported by the investigator to the CureGN DCC will be reviewed. The DCC may
527 request additional information from sites for analysis of these events. Sites will report SAEs
528 related to the study according to the time frames outlined below.

529

530 All events that are serious and related (possibly or probably) to the observational study must be
531 reported to the DCC within 24 hours of the investigator being informed of the event. Follow-up
532 information about a previously reported serious and related AE may be reported to the DCC
533 within 7 working days of the investigator receiving the information; however, important follow-
534 up information must be submitted within 24 hours. All deaths related to a study procedure must
535 be reported to the DCC within 24 hours of the investigator being informed of the event.

536

537 5.2. BENEFITS TO THE PATIENTS

538 There are no direct benefits to subjects for participation in the study. Potential benefits include the
539 satisfaction of altruism and detection of new information that may improve the management of patients
540 with glomerular diseases in the future.

541 5.2.1 Inclusion of Women

542

543 This is a multi-center study drawing on a clinical population from PCCs in the United States, Canada, and
544 Europe. Women will be recruited into the study. It is envisioned that the representation of women will
545 correspond to the fraction of women in the population diagnosed with biopsy confirmed primary
546 glomerular diseases emanating from FSGS, MCD, IgAN, and MN. Special efforts will be incorporated into
547 the recruitment process to facilitate the optimal inclusion of women with these diseases in the study.

548 5.2.2 Inclusion of Minorities

549

550 Racial and ethnic minority groups will be recruited into the study. It is envisioned that the
551 representation of persons comprising racial and ethnic minority groups will correspond to the fraction of
552 those groups in the population diagnosed with biopsy confirmed primary glomerular diseases emanating
553 from FSGS, MCD, IgAN, and MN. Special efforts will be incorporated into the recruitment process to
554 facilitate the optimal inclusion of persons of racial and ethnic minority groups. Recruitment will be
555 monitored to ensure adequate representation of minority groups.

556
557
558
559
560
561
562
563
564
565
566
567
568
569
570
571
572
573
574
575
576
577
578
579
580
581
582
583
584
585
586
587
588
589
590
591
592
593
594
595
596
597
598
599
600
601
602
603

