 332 more than 40 sites coordinated by the four PCCs; (2) 800 patients will be recruited per year over 3 years,
 333 resulting in an average follow-up of 2 years during the first 4-year data collection phase; and (3) assume
 334 a loss of 10% of the available follow-up due to patient loss of follow-up. Additional assumptions include:
 335 a power of 80%, an alpha of 0.05, an intra-cluster correlation of 0.05, and a between-facility normalized
 336 standard deviation of the sample size of 0.15. Power is computed for a range of sample sizes,
 337 representing subgroup comparisons such as within and between diagnosis groups (FSGS, MCD, MN,
 338 IgAN), among pediatric patients, and comparisons with control populations. The statistical power for
 339 time-to-event analyses are calculated as the minimum detectable hazard ratio (MDHR) associated with
 340 comparisons between equal numbers of patients, i.e., 50% exposure, out of the number shown in the
 341 column headings of Table D. Study durations of 4 and 20 years correspond to the first phase of the study
 342 and to potential future phases. Event rates are derived from results in published literature, including
 343 examples of ESKD/death rates for FSGS of 0.03²⁴ and 0.05²⁵ per patient-year, IgAN around 0.03^{25,26}, and
 344 MN of 0.01²⁷ and 0.02²⁵; proteinuria reduction (remission) rates for FSGS of 0.18²⁴ and for MN of 0.23²⁷;
 345 and rates of a 50% drop in estimated glomerular filtration rate (eGFR, progression) for MN of 0.04²⁸.
 346 These rates are not outcome-specific; any analysis of an event with a similar rate on the data described
 347 would have the MDHR indicated in Table D.
 348
 349
 350
 351
 352

Table D: Minimum Detectable Hazard Ratios by Observation Period, Expected Event Rate, and Cohort Size						
Outcome	Study Duration (avg. patient years)	Rates	300 (150/Gro up)	600 (300/Gro up)	1200 (600/Gro up)	2400 (1200/Gro up)
ESKD/death	4 year (2 yrs)	.01- .04	>10	>10-7.4	>10-4.5	>10-3.6
	20 year (17 yrs)	.01- .04	>10-2.6	5.9-2.0	4.0-1.8	3.3-1.6
50% eGFR (progression)	4 year	.04- .12	>10-3.2	7.3-3.4	4.5-2.0	3.6-1.9
	20 year	.04- .12	2.5-1.8	2.0-1.6	1.8-1.5	1.7-1.4
Proteinuria (remission)	4 year	.18- .23	2.4-2.2	2.0-1.8	1.8-1.7	1.7-1.6
	20 year	.18- .23	1.7-1.6	1.5-1.5	1.4-1.4	1.4-1.3

353
354
355
356
357
358
359
360
361
362
363
364
365
366
367
368
369
370
371
372
373
374
375
376
377
378
379
380
381
382
383

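### Section 4.5 charges the power for clustering by site, but section 4.6 names no center effect for the longitudinal and Cox models; tests of predictors that differ between centers would reject too often

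*Protocol*

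**What the plan says.** Protocol section 4.5 lists its power assumptions as "a power of 80%, an alpha of 0.05, an intra-cluster correlation of 0.05, and a between-facility normalized" "standard deviation of the sample size of 0.15", with data from "more than 40 sites coordinated by the four PCCs" and "800 patients will be recruited per year over 3 years". The power that follows (Table D) is for time-to-event comparisons, given as minimum detectable hazard ratios.

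Section 4.6 then allots model terms by family of analysis:
- **Cross-sectional and retrospective case-control analyses:** logistic regression and "a mixed model approach with center as a random effect", with between-center differences given as the reason.
- **Longitudinal models for progression measures such as eGFR:** "Patient-level identifiers will be included as a random effect in these models". No center effect is named, and the text does not say whether the patient effect is an intercept alone or includes a slope.
- **Time-to-event outcomes:** time-to-"event Cox regression models will be used when analyzing defined outcomes and will use left truncation". No frailty, stratification or clustered variance by center is named.

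The same section lists eGFR slope among the outcomes. Section 4.1.1 names four center networks, one of them a pediatric consortium.

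**The concern.** The analyses whose power is reduced for clustering are the Cox analyses, and these are described without any means of accounting for it. The protocol does assign center to a model, but to a different family. An analyst who follows section 4.6 literally would fit a patient effect alone, or an ordinary Cox model, and treat patients from one site as independent.

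That does harm when the predictor also varies by site. Age group is partly an attribute of the network, because of the pediatric consortium, and section 4.5 names pediatric and between-diagnosis comparisons among those to be powered. Treatment practice and race or ethnicity may also vary by site, but the protocol gives no figures on this. For such predictors the intervals would be too narrow and some reported associations would be false positives.

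**Working it through.** **1. Does the correlation of 0.05 really enter Table D?**

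Inputs from section 4.5: 80% power, alpha 0.05 (taken as two-sided), equal groups, average follow-up of 2 years less 10%, so 1.8 years. The value 0.15 is read as the coefficient of variation of site size. Forty sites are used, so m = N/40.

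Design effect: DE = 1 + [(1 + 0.15²)m − 1] × 0.05. At N = 2,400, m = 60 and DE = 1 + (61.35 − 1) × 0.05 = 4.02.

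Freedman's formula needs 7.85 × [(HR + 1)/(HR − 1)]² events. The stated rate is applied to the higher-rate group, rate/HR to the other, and group sizes are divided by DE.

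| 4-year row | N | Table D | With DE | Without clustering |
|---|---|---|---|---|
| Remission, rate 0.18 | 300 / 600 / 1200 / 2400 | 2.4 / 2.0 / 1.8 / 1.7 | 2.43 / 1.96 / 1.74 / 1.63 | 2.09 / 1.63 / 1.39 / 1.26 |
| ESKD/death, rate 0.04 | 600 / 1200 / 2400 | 7.4 / 4.5 / 3.6 | 7.0 / 4.2 / 3.3 | 3.3 / 2.1 / 1.6 |

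Table D is not reproduced exactly. These rows come close only with the clustering included, and with the full design effect, which is the one for an exposure that varies only between sites.

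**2. What happens if the analysis then ignores center?**

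Let ρ be the within-site correlation of the predictor. This is assumed; the protocol gives no value. The variance is understated by DE(ρ) = 1 + [(1.0225)m − 1] × 0.05 × ρ, and the true error of a nominal 5% test is 2 × [1 − Φ(1.96/√DE)].

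Example, N = 2,400, 40 sites, ρ = 0.2: DE = 1 + 60.35 × 0.05 × 0.2 = 1.60, √DE = 1.27, 1.96/1.27 = 1.55, error 12%.

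| Sites, N | m | ρ = 0 | ρ = 0.2 | ρ = 0.5 | ρ = 1 |
|---|---|---|---|---|---|
| 40, 2400 | 60 | 5% | 12% | 22% | 33% |
| 80, 2400 | 30 | 5% | 9% | 14% | 21% |
| 40, 600 | 15 | 5% | 7% | 9% | 13% |
| 80, 600 | 7.5 | 5% | 6% | 7% | 9% |

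At ρ = 1, N = 2,400 and 40 sites, the correct standard error is √4.02 = 2.0 times the naive one.

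A simulation (40 sites of 60 patients, correlation 0.05, 4,000 runs) agrees: 11.8% at ρ = 0.2 and 32% for a predictor wholly between centers. It gives 4.5% for a predictor independent of center and 3.8% for one balanced within center.

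**3. Separate check: intercept only, when slopes vary.**

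Assumed, not from the protocol: patient slope SD 3 mL/min per year and residual SD 8 mL/min. Let S be the sum of squared visit times about their mean, for n visits. The true variance of a patient's fitted slope is 3² + 8²/S. An intercept-only model uses [8² + 3² × S/(n − 1)]/S.

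- Seven four-monthly visits over 2 years: S = 3.11; true 29.6, model 22.1, ratio 0.75; error 9%.
- Thirteen visits over 4 years: S = 20.2; true 12.2, model 3.9, ratio 0.32; error 27%.
- Three visits at years 0, 1 and 2: S = 2; true 41, model 36.5, ratio 0.89; error 6%.

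**The case against.** The strongest objection is that section 4.6 is illustrative and silent, not exclusive. It never says that center will be left out, and frailty terms or robust variances are often settled in an analysis plan, which is not at hand. A reader might infer that the protocol has decided against a center effect; the text does not support that. What remains is that the protocol chose to name random effects model by model, gave center to one family and the patient to another, and so does not match its own power section.

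A reader might also infer that standard errors will be too small throughout. They will not. For predictors unrelated to center, or balanced within it, the naive standard error is about right or slightly conservative.

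The size depends on inputs that the protocol does not fix. It says more than 40 sites, and more sites shrink the effect. Section 3 has each aim addressed for each disease, and section 4.1.1 plans about 600 patients per disease, so the N = 600 rows are often the relevant ones.

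The slope point does not follow from the site correlation, and calling the patient effect an intercept only is one reading: a patient random effect can include a slope. The 27% needs the full 4-year schedule, whereas section 4.5 expects 2 years on average.

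Finally, stratifying the Cox model by center is no general cure. It cannot estimate a predictor that varies only between sites. Events can also be few: 600 patients × 1.8 years × 0.01 is about 11 events over more than 40 sites. This objection stands and limits the remedy.

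**Conclusion.** The concern holds for predictors that differ between centers. Section 4.5 pays for clustering in its detectable hazard ratios, and section 4.6 as written does not carry it into the Cox models or the longitudinal models.

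At the plan's own correlation of 0.05, the inflation runs from slight (6% to 7% at N = 600, ρ = 0.2) to serious (33% at N = 2,400 and 40 sites for a wholly site-level predictor). There is none for predictors unrelated to center. These figures rest on assumed predictor correlations, on the 0.05 applying to the outcome analyzed, and on a design-effect approximation applied to patient-level comparisons.

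The random-slope point is a smaller, separate clarification. Its illustrative size is 9% at 2 years of four-monthly visits, under assumed standard deviations.

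**What to change.** In section 4.6:
- **Longitudinal models:** add a center random effect to the patient effect.
- **Cox models:** use a shared center frailty or a center-clustered robust variance. Allow stratification by center only for predictors that vary within center, and only when events per center are adequate. With very few events a clustered variance is itself unreliable, so say which option applies then.
- **eGFR-slope and predictor-by-time analyses:** state a patient random slope as well as a random intercept.
- **Confounding by site:** note that a clustered variance corrects the standard error but does not remove such confounding, and that a random effect does so only in part.

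The change needs a few sentences and model code, and no new data. Intervals become somewhat wider for center-clustered predictors, which is the price that section 4.5 already assumes.

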120 profile, and their impact on disease presentation and clinical outcome; study gene-gene and gene-
121 environment interactions that contribute to the development of the four glomerulopathies; and
122 devise systems genetics approach to clarify pathogenesis.

123 **4. Aim 4 (PROs).** To identify Patient Reported Outcomes (PROs, e.g., symptom burden, physical
124 function, quality of life) associated with primary glomerular diseases; to validate disease-specific
125 instrument(s) to assess the impact of disease and its therapy on patients; and to test the
126 associations of PROs with disease progression.

127

128

129

130

131

132

133 **4. INVESTIGATION PLAN**

134 4.1. STUDY METHODS

135 **4.1.1 Overview**

136 The core CureGN study is a multi-center prospective cohort study of approximately 2,400 adult and
137 pediatric patients with biopsy-documented IgAN, FSGS, MN, and MCD. For each disease category,
138 approximately 600 participants will be recruited. Participants will be recruited concurrently from each of
139 the four Participating Clinical Center (PCC) networks: Columbia University, Midwest Pediatric
140 Nephrology Consortium, University of North Carolina, and University of Pennsylvania. Each PCC
141 represents multiple clinical sites, with current representation in the United States, Canada, and Italy.
142 Participants meeting the enrollment criteria below will be enrolled if they or their legally authorized
143 representative(s) provide signed informed consent. Patients will be followed until death, withdrawal
144 from the study, or end of study. For the initial funding period, total study duration is approximately 4
145 years. Participant recruitment may occur at any point during the study period, and at least until
146 recruitment goals are met for each disease category.

147

148 4.2. PARTICIPANT SELECTION

149 **4.2.1 Inclusion Criteria**

- 150 • Diagnosis of MCD, FSGS, MN, or IgAN on first diagnostic kidney biopsy, as per specified
- 151 pathology definitions
- 152 • First diagnostic kidney biopsy within 5 years of study enrollment
- 153 • Access to first kidney biopsy report and/or slides
- 154 • All ages
- 155 • Willingness to comply with study requirements, including intention to fully participate in
- 156 protocol-specified follow-up at a clinical study site
- 157 • Informed consent and, where age appropriate, informed assent

158

159 **4.2.2 Exclusion Criteria**

- 160 • ESKD, defined as chronic dialysis or kidney transplant

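### Section 4.6 selects biomarkers on outcome and then tests the resulting panels against outcome without naming separate participants or nested selection, so a panel test in the selection data would add no evidence.

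*Protocol*

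**What the plan says.** The last paragraph of Protocol section 4.6 describes, as an example, how molecular biomarkers would be analysed:

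1. **Purpose.** To screen a "large number of potential predictors without losing analytical power, analyses will be performed in a" "hypothesis-generating manner. Regression analysis will be performed to obtain p-values for the" association of outcome with a biomarker.
2. **Selection.** The screen is on the "association of outcome with a biomarker, and a threshold value of false discovery rate would be set to" define the pool of candidates. No threshold value and no number of candidates is given.
3. **Grouping.** The rule is used to "determine a pool of potentially important biomarkers. Selected biomarkers will be analyzed and" grouped by biological function.
4. **Panel step.** "Panels will be further tested for the" "association with outcome via ridge regression".

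The paragraph mentions no hold-out sample, cross-validation, permutation or external cohort. The one separation rule in section 4.6 concerns longitudinal predictors. It keeps the period in which a predictor is measured apart from the follow-up for the outcome, and it does not separate participants. The study is a single cohort. Section 4.1.1 says that for each disease "approximately 600 participants will be recruited", about 2,400 in all.

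**The concern.** Steps 2 and 4 both concern association with outcome. A marker enters a panel because its association was strong in the data at hand. If step 4 uses those data again, the panel is tested on the property by which its members were chosen. Ridge regression shrinks coefficients, but it does not allow for how the markers came to be in the model. False discovery rate control applies to the list of single markers and gives no error rate for a later test on groups of survivors.

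A reader would take a further test as added support for a panel, and here it would give none. Aim 2 in section 3 looks to biomarkers that may be used in practice or in trials. A panel p-value and fit taken from the selection data could carry a false or overstated signal into that work.

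**Working it through.** The protocol gives no figure for this analysis, so there is none to reproduce.

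**Inputs from the protocol.** About 600 participants per disease and 2,400 in total (section 4.1.1). From section 4.5: "a power of 80%, an alpha of 0.05, an intra-cluster correlation of 0.05, and a between-facility normalized" standard deviation of 0.15, of which only the power and alpha are used here, with two-sided tests assumed.

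**Assumed inputs.** 1,000 independent candidate markers, a continuous outcome, Benjamini-Hochberg selection at q = 0.05, 0.10 or 0.25, ten function groups, and a ridge penalty of 0.1n.

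**Step 1: why the second test can hardly fail.** If Benjamini-Hochberg keeps k of m markers, every kept marker has p ≤ kq/m. With m = 1,000, q = 0.25 and k = 20, the bound is 20 × 0.25/1,000 = 0.005. For the bound to exceed 0.05, k must exceed 0.05 × 1,000/0.25 = 200 markers at q = 0.25, or 500 at q = 0.10. At q = 0.05 it never does. So unless a large share of the candidates is kept, each panel member is already well below 0.05 in the data about to be used again.

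**Step 2: simulation with ridge.** Each panel was tested at 0.05 by a permutation test of the ridge fit, once in the selection data and once with selection in one half and the test in the other. Scenarios were a global null (N = 600, 600 runs per q) and 20 true markers (N = 600 and N = 2,400, 60 runs per q). The table counts panels made only of null markers.

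| Scenario | q | Positive, same data | Positive, held-out half |
|---|---|---|---|
| Global null, N = 600 | 0.05 | 35/35 | 1/20 |
| | 0.10 | 65/65 | 2/59 |
| | 0.25 | 293/293 | 12/225 |
| 20 true, N = 600 | 0.05 | 51/51 | 0/26 |
| | 0.10 | 73/73 | 1/55 |
| | 0.25 | 218/218 | 4/185 |
| 20 true, N = 2,400 | 0.05 | 51/51 | 0/24 |
| | 0.10 | 85/85 | 3/64 |
| | 0.25 | 229/229 | 7/192 |
| **Total** | | **1,100/1,100 (100%)** | **30/850 (3.5%)** |

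**Step 3: how often a panel forms.** Under the global null with no split, at least one panel formed in 5.3%, 8.7% and 26.5% of runs at q = 0.05, 0.10 and 0.25. With 20 true markers, the false share of the selected markers stayed near q (about 6%, 9% and 25%). The screen therefore does its job, and the fault lies in the panel test that follows.

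**Step 4: inflation of fit.** A separate simulation used n = 600, 1,000 independent markers, 20 true effects of 0.15 SD, q = 0.20 and unpenalised regression. The R-squared of all selected markers together was 0.27 in the selection data and 0.12 in new participants.

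**Step 5: cost of a half split.** The correlation detectable with 80% power at two-sided 0.05 is r = tanh[(1.960 + 0.842)/√(n − 3)].

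- N = 600: tanh(2.802/√597) = 0.114; N = 300: tanh(2.802/√297) = 0.161.
- N = 2,400: 0.057; N = 1,200: 0.081.

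For ESKD or death within one disease, section 4.5 assumes 2 years' average follow-up with 10% lost, and Table D uses rates of .01 to .04. That gives 600 × 2 × 0.9 × 0.01 = 10.8 to 600 × 2 × 0.9 × 0.04 = 43.2, or about 11 to 43 events. Halving leaves about 5 to 22.

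**The case against.** **Use of the same participants is inferred.** A reader might take the protocol to say that panels are tested in the people used for selection. It does not say so, and an analysis plan or ancillary protocol could add a split. This stands as a limit on the point. Still, the protocol does not defer the method. It fixes the order of steps and names the last estimator, in a single cohort, with the stated wish not to lose power. Reuse of the data is the natural reading.

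**The work is exploratory.** The paragraph is offered as an example and labelled hypothesis-generating, and it states no panel alpha or decision rule. That lowers the stakes. It excuses a lenient screen but does not make a second look at the same data informative.

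**Nearly always positive is too strong for the whole procedure.** A reader might infer that the pipeline nearly always yields a positive panel. The documents do not support this. Selection is by a false discovery rate threshold, not by taking a fixed number of top markers, so under a global null most runs produce no panel. The statement holds only once a panel exists.

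**Null-only panels are picked with knowledge of the truth.** In practice many panels would mix real and false markers. That is fair. The comparison shows that the same-data test cannot tell a wholly false panel from a real one. It does not show how common false panels would be.

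**Aim 2 does not mention panels.** It would be too much to call them its product, and the panel sentence speaks of association, not prediction. The inflation of fit matters only if predictive measures for panels are reported from the selection data.

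**Conclusion.** The point holds in conditional form. Section 4.6 sets out selection on outcome followed by a test against outcome, and states no separation of participants or nesting of the selection. If both steps use the same data, a panel that has been formed is almost certain to test positive whether or not its markers are real: 100% of null-only panels, against about 3.5% in a held-out half. The p-value then adds nothing to the screen, and apparent fit is too high.

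The exact percentages rest on assumed inputs: 1,000 independent markers, q of 0.05 to 0.25, ten groups and a continuous outcome. The direction follows from the selection rule as long as only a small share of candidates is kept (step 1). The remedy is cheap and worth making. The conduct of the cohort and its other analyses are not affected.

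**What to change.** Add a short statement to section 4.6, choosing one of these:

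- **Nested resampling.** Panel p-values and predictive measures come from permutation or cross-validation that repeats the whole screen, grouping and ridge sequence each time. Function groups are assigned from an annotation set in advance, so that the grouping can be repeated. The cost is computing time and the work of automating the grouping.
- **Separate participants.** Panels are tested only in participants not used for screening, where event numbers allow. A half split raises the detectable correlation from 0.114 to 0.161 at N = 600. It suits rare outcomes poorly: about 5 to 22 ESKD or death events would remain per half within a disease, and Table D already gives a minimum detectable hazard ratio above 10 for 300 patients at 4 years.
- **Descriptive label.** The ridge step is called descriptive, and no panel p-value is reported from the selection data. This costs nothing in power or computing, but the panels then await testing elsewhere.
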